5.1.1 Estimand

The primary estimand is defined by the following:

- Population: Subjects in the ITT population as defined by protocol eligibility criteria.
- Variable: the proportion of subjects with a ≥ 2 -point improvement in the IGA score at Week 12 compared to baseline.
- The following intercurrent events and their handling include:
 - Treatment discontinuation prior to Week 12 due to adverse event or lack of efficacy: Composite variable strategy, where the discontinuation may be considered informative about the subject's outcome and will therefore consider these subjects as non-responders.
 - Modification to dose level: Treatment policy strategy, where results will be used regardless of dose modifications.
 - Use of prohibited medication: Composite variable strategy, where the use of such medication may be considered informative about the subject's outcome (e.g., subjects are using prohibited medications due to perceived lack of efficacy of study drug) and will therefore consider these subjects as non-responders.
- Population-level summary: The difference in proportions of subjects achieving IGA response at Week 12 between treatment groups (TMB-001 0.05% and vehicle).

5.1.2 Primary Analysis Methods

The difference in proportion of subjects achieving IGA treatment success at Week 12 (Visit 6) between the TMB-001 0.05% and vehicle groups will be the primary efficacy endpoint. For this endpoint, the IGA score will be dichotomized to "responder" (treatment success) or "non-responder" (treatment failure), where a responder is defined as at least a 2-grade improvement (decrease) in severity in the IGA score as compared to baseline. Inference will be made by comparing the proportions of

treatment successes in the TMB-001 0.05% group vs the vehicle group at Week 12 using the CMH test stratified by age (≥ 17 , 12-16 and 6-11) and genetic subtype. A two-sided alpha of 0.01 will be used for significance testing, along with 99% and 95% confidence intervals.

Missing Week 12 data will be imputed, as outlined in Section 3.9.1, and IGA responder status will be derived from the imputed values. A CMH analysis will be performed on each of the 50 imputed datasets. The results from the CMH analyses will be combined using the Wilson-Hilferty transformation by Ratitch et al. (Ratitch et al. 2013) to produce a pooled CMH statistic and p-value. The differences in proportions and standard errors will be combined using Rubin's Rule (Little 2019) the SAS PROC MIANALYZE. The pooled Mantel-Haenszel stratum-weighted estimator of the difference in proportion and the associated standard error will be used to produce the 99% confidence interval based on the large-sample approximation method for binary data without using continuity correction. The 95% confidence interval will also be provided.

A summary of the occurrences of intercurrent events of each type will be provided by treatment group.

5.1.3 Sensitivity Analysis Methods

The following sensitivity analyses are planned to show the robustness of the primary analysis:

- 1) The primary analysis will be repeated using the PP population (using the same CMH test and the same MCMC multiple imputation method).
- 2) The primary analysis will be repeated using the set of subjects with non-missing Week 12 IGA assessment using both the ITT and PP populations (i.e., a completer's analysis).
- 3) The primary analysis will be repeated on both the ITT and PP populations by imputing missing Week 12 data using last observation carried forward (LOCF).
- 4) A tipping point analysis will be performed using the observed data to assess the potential impact of missing Week 12 IGA scores on the primary analysis result.

The following steps will be followed to implement the tipping point analysis:

- a. Determine the number of missing IGA scores at Week 12 in the TMB-001 0.05% treatment group (n_{1m}) and Vehicle group (n_{2m}) in the ITT population
- b. Let s_1 represent the number of IGA responders in missing TMB-001 0.05% group. Let s_2 represent the number of IGA responders in the Vehicle group
- c. Set both $s_1 = 0$ and $s_2 = 0$
- d. From 0 to n_{1m} , calculate the difference in proportions and corresponding p-value of the difference between the treatment groups, where each iteration is $s_1 = s_1 + 1$, using a CMH test

- e. From 0 to n_{2m} , calculate the difference in proportions and corresponding p-value of the difference between the treatment groups, where each iteration is $s_2 = s_2 + 1$, using a CMH test
- f. Present the p-value from each analysis combination of s_1 and s_2 in steps (d) and (e) in a matrix (e.g. a heatmap)
- g. Determine the “tipping point” of the results where the difference in proportions is significant at the 0.01 level

5) The primary analysis will be repeated on the ITT population by imputing missing Week 12 IGA scores on the basis of a pattern-mixture model under the missing not at random (MNAR) assumption. Specifically, a control-based pattern imputation will be performed, as described by Ratitch and O’Kelly (Ratitch and O’Kelly 2011).

6) Treatment effect will be analyzed via generalized estimating equations (GEEs) using SAS PROC GENMOD, with IGA response as the dependent variable, and treatment group, age group, CI type, visit, and treatment by visit interaction as independent variables. Week 12 odds ratios and 95% confidence intervals will be provided.

7) If there are discrepancies between the CI subtypes reported in the IRT and those reported in the EDC, the primary analysis will be repeated using the CI subtypes reported in the IRT rather than those reported in the EDC.

5.2 Key Secondary Efficacy Analysis

All analyses in this section will be presented as described in Section 3.11.2, unless otherwise indicated. All analyses will be primarily performed using the ITT population, unless otherwise noted.

5.2.1 Estimands

The estimands of the key secondary endpoints can be written out in a similar manner as the estimand of the primary endpoint. High-level descriptions of estimands are outlined in the following table:

Table 1. Attributes of Estimands for Key Secondary Endpoints

Endpoint		
Difference in proportions of subjects with IGA-scores of clear/almost clear	Difference in proportions of subjects with ≥ 2 -point change IGA-scaling severity sub-scores	Difference in proportions of subjects with ≥ 4 -point improvement in worst Itch-QoL

Population	Subjects in the ITT population as defined by protocol eligibility criteria	Subjects in the ITT population as defined by protocol eligibility criteria	Subjects in the ITT population as defined by protocol eligibility criteria with baseline WI-NRS of ≥ 7
Variable	Proportion of IGA clear/almost clear score responders	Proportion of IGA-scaling sub-score responders	Proportion of worst Itch-QoL responders
Intercurrent Events and Strategies	1) Composite variable strategy for treatment discontinuations due to adverse event or lack of efficacy 2) Treatment policy strategy for dose modifications 3) Composite variable strategy for use of prohibited medications		
Population-level Summary	The difference in proportions of subjects achieving responses at Week 12 between the TMB-001 0.05% and vehicle treatment groups		

5.2.2 Analysis Methods

Statistical testing will be performed on the key secondary efficacy endpoints using a two-side alpha of 0.01, according to the following hierarchical order.

5.2.2.1 IGA Clear Score Responders at Week 12

The difference in proportions of subjects with IGA score of clear or almost clear (henceforth referred to as 'IGA clear score responders') versus mild/moderate/severe will be computed at Week 12, between the TMB-001 0.05% and vehicle treatment groups.

The difference in proportions will be calculated in a similar manner as the primary efficacy endpoint using the CMH test, including the use of 50 multiply imputed datasets combined using the Wilson-Hilferty transformation for the pooled CMH statistic and Mantel-Haenszel stratum-weighted difference in proportions combined using Rubin's rule. Results will be provided using the primary efficacy data presentation.

5.2.2.2 IGA-Scaling Sub-Score Responders at Week 12

The difference in proportions of subjects with a ≥ 2 point change from baseline in IGA-scaling severity sub-scores (henceforth referred to as 'IGA-scaling sub-score responders') will be computed at Week 12 among subjects who have a score of ≥ 3 at baseline, between the TMB-001 0.05% and vehicle treatment groups.

The difference in proportions will be calculated in a similar manner as the primary efficacy endpoint using the CMH test, including the use of 50 multiply imputed datasets combined using the Wilson-Hilferty transformation for the pooled CMH statistic and Mantel-Haenszel stratum-weighted difference in proportions combined using Rubin's rule. Results will be provided using the primary efficacy data presentation.

5.2.2.3 Worst Itch-QoL (WI-NRS) Responders at Week 12

The difference in proportions of subjects achieving a ≥ 4 -point improvement from baseline in weekly Worst Itch-QoL scores on the WI-NRS (henceforth referred to as 'Worst Itch-QoL (WI-NRS) responders') will be computed at Week 12, between the TMB-001 0.05% and vehicle treatment groups. Only subjects with baseline WI-NRS scores of ≥ 7 will be included in this analysis.

The WI-NRS scores will be collected daily, where the weekly average scores will be mapped to each protocol-specified visit and used for analysis, as appropriate. The daily scores to be used will depend on actual visit dates; daily scores of the 6 days prior to the Week 12 visit will be averaged with the daily score reported on the Week 12 visit date to create the weekly average for the Week 12 visit. A weekly average can only be computed if there are ≥ 4 daily scores reported, otherwise the weekly score will be considered missing. Early subjects do not have daily scores collected prior to baseline (in order to derive baseline weekly averages). In such cases, the single baseline score will be used for analysis.

The difference in proportions will be calculated in a similar manner as the primary efficacy endpoint using the CMH test, including the use of 50 multiply imputed datasets combined using the Wilson-Hilferty transformation for the pooled CMH statistic and Mantel-Haenszel stratum-weighted difference in proportions combined using Rubin's rule. Results will be provided using the primary efficacy data presentation.

For completeness, a descriptive analysis of the I-NRS will also be provided, as applicable.

5.2.3 Sensitivity Analysis Methods

Sensitivity analyses of all key secondary endpoints will include:

- 1) Repeat analyses using the PP population (using the same CMH test and the same MCMC multiple imputation method).
- 2) Repeat analyses using the set of subjects with non-missing Week 12 data using both the ITT and PP populations (i.e., a completer's analysis).
- 3) If there are discrepancies between the CI subtypes reported in the IRT and those reported in the EDC, the key secondary analyses will be repeated using the CI subtypes reported in the IRT rather than those reported in the EDC.

5.3 Other Secondary Efficacy Analysis

5.3.1 Estimands

The estimands of the other secondary endpoints can be written out in a similar manner as the estimands of the key secondary endpoints. High-level descriptions of estimands are outlined in the following table:

Table 2. Attributes of Estimands for Other Secondary Endpoints

Endpoint					
	Difference in proportions of subjects with VIIS-scaling score reduction of 50%	Difference in proportions of subjects with VIIS-scaling score reduction of 25%	Difference in proportions of subjects with ≥2-point improvement in IGA fissuring sub-scores	Difference in proportion of subjects with ≥2-point improvement in IGA score, IGA scaling and fissuring sub-scores	Difference in proportions of subjects with VIIS-scaling score reduction of 50%
Population	Subjects in the ITT population as defined by protocol eligibility criteria	Subjects in the ITT population as defined by protocol eligibility criteria	Subjects in the ITT population as defined by protocol eligibility criteria with baseline fissuring sub-score of ≥3	Subjects in the ITT population as defined by protocol eligibility criteria with baseline scaling/fissuring sub-score of ≥3	Subjects in the ITT population as defined by protocol eligibility criteria
Variable	Proportion of VIIS 50% reduction responders among areas with baseline VIIS score ≥3	Proportion of VIIS 25% reduction responders among areas with baseline VIIS score ≥3	Proportion of worst IGA fissuring sub-score responders	Proportion of IGA responders, /IGA scaling sub-score responders, IGA fissuring sub-score responders	Proportion of VIIS 50% reduction responders among areas with baseline VIIS score ≥3
Intercurrent Events and Strategies	1) Composite variable strategy for treatment discontinuations due to adverse event or lack of efficacy 2) Treatment policy strategy for dose modifications 3) Composite variable strategy for use of prohibited medications				
Population-level Summary	The difference in proportions of subjects achieving responses at Week 12 between the TMB-001 0.05% and vehicle treatment groups			The difference in proportions of subjects achieving responses at Week 24 between the TMB-001 0.05% BID and QD dosing groups	

5.3.2 Analysis Methods

All analyses in this section will be presented as described in Section 3.11.2, unless otherwise indicated. All analyses will be primarily performed using the ITT population, unless otherwise noted. No formal inference is intended to be performed on other secondary efficacy endpoints, however 95% confidence intervals will be provided. The estimand framework will be applied for all analyses using multiple imputation.

5.3.2.1 VIIS-Scaling Score 50% Reduction Responders at Week 12

The difference in proportions of subjects achieving at least a 50% reduction on average from baseline in VIIS-scaling score in all areas with baseline VIIS score ≥ 3 will be computed at Week 12 along with 95% confidence intervals, between the TMB-001 0.05% and vehicle treatment groups. The difference in proportions will be calculated in a similar manner as the primary efficacy endpoint using the CMH test, including the use of 50 multiply imputed datasets combined using the Wilson-Hilferty transformation for the pooled CMH statistic and Mantel-Haenszel stratum-weighted difference in proportions combined using Rubin's rule. Only the areas with baseline VIIS scores of ≥ 3 will be included in this analysis. Areas may include the upper back, the upper arm, the shin/lower leg, and the dorsal foot. Individual areas may reach a 50% reduction; however, subjects will be considered responders only if the average of all areas with baseline VIIS scores of ≥ 3 achieve a 50% reduction.

The analysis will be repeated using observed data only. The Mantel-Haenszel stratum-weighted estimator of the difference in proportion and the associated standard error will be used to produce a 95% confidence interval.

Results will be provided using the primary efficacy data presentation.

This analysis will be repeated using the PP population.

5.3.2.2 VIIS-Scaling Score 25% Reduction Responders at Week 12

The difference in proportions of subjects achieving at least a 25% reduction on average from baseline in VIIS-scaling score in all areas with baseline VIIS score ≥ 3 at Week 12 between TMB-001 0.05% and vehicle treatment groups will be computed in a similar manner as the primary efficacy endpoint using the CMH test, including the use of 50 multiply imputed datasets combined using the Wilson-Hilferty transformation for the pooled CMH statistic and Mantel-Haenszel stratum-weighted difference in proportions combined using Rubin's rule., along with 95% confidence intervals. Individual areas may reach a 25% reduction; however, subjects will be considered responders only if the average of all areas with baseline VIIS scores of ≥ 3 achieve a 25% reduction.

The analysis will be repeated using observed data only. The Mantel-Haenszel stratum-weighted estimator of the difference in proportion and the associated standard error will be used to produce a 95% confidence interval.

Results will be provided using the primary efficacy data presentation.

5.3.2.3 IGA-Fissuring Sub-Score Responders at Week 12

The difference in proportions of subjects with a ≥ 2 point change from baseline in IGA-fissuring severity sub-scores will be computed at Week 12 among subjects who have a score of ≥ 3 at baseline, between the TMB-001 0.05% and vehicle treatment groups will be computed in a similar manner as the primary efficacy endpoint using the CMH test, including the use of 50 multiply imputed datasets combined using the Wilson-Hilferty transformation for the pooled CMH statistic and Mantel-Haenszel stratum-weighted difference in proportions combined using Rubin's rule., along with 95% confidence intervals.

The analysis will be repeated using observed data only. The Mantel-Haenszel stratum-weighted estimator of the difference in proportion and the associated standard error will be used to produce a 95% confidence interval.

Results will be provided using the primary efficacy data presentation.

This analysis will be repeated using the PP population.

5.3.2.4 IGA Score, IGA Scaling Sub-Score, and IGA Fissuring Sub-score Responders at Week 24

The difference in proportions of subjects achieving a ≥ 2 grade improvement from baseline in the IGA score, the IGA Scaling sub-score, and IGA fissuring sub-score will each be computed at Week 24, between the TMB-001 0.05% BID and QD maintenance dosing groups will be computed in a similar manner as the primary efficacy endpoint using the CMH test, including the use of 50 multiply imputed datasets combined using the Wilson-Hilferty transformation for the pooled CMH statistic and Mantel-Haenszel stratum-weighted difference in proportions combined using Rubin's rule., along with 95% confidence intervals.

The analyses will be repeated using observed data only. The Mantel-Haenszel stratum-weighted estimator of the difference in proportion and the associated standard error will be used to produce a 95% confidence interval.

Results will be provided using the open-label dosing efficacy data presentation.

These analyses will be repeated using the PP population.

5.3.2.5 VIIS-Scaling Score 50% Reduction Responders at Week 24

The difference in proportions of subjects achieving at least a 50% reduction on average from baseline in VIIS-scaling score in all areas with baseline VIIS score ≥ 3 at Week 24 between TMB-001 0.05% BID and QD maintenance dosing groups will be computed in a similar manner as the primary efficacy endpoint using the CMH test, including the use of 50 multiply imputed datasets combined using the Wilson-Hilferty transformation for the pooled CMH statistic and Mantel-Haenszel stratum-weighted difference in proportions combined using Rubin's rule., along with 95% confidence intervals. Individual areas may reach a 50% reduction; however, subjects will be considered responders only if the average of all areas with baseline VIIS scores of ≥ 3 achieve a 50% reduction. The analysis will be repeated using observed data only. The Mantel-Haenszel stratum-weighted estimator of the difference in proportion and the associated standard error will be used to produce a 95% confidence interval.

Results will be provided using the open-label dosing efficacy data presentation.

5.4 Patient-Reported Outcomes Analysis

All analyses in this section will be presented as described in Section 3.11.2, unless otherwise indicated. All analyses will be primarily performed using the ITT population, unless otherwise noted. No formal inference is intended to be performed on patient-reported outcomes.

5.4.1 IQoL-32 Responders at Week 12 and Week 24

The IQoL-32 contains 32 items, each scored from 0 to 4 ('not applicable', 'not at all', 'a little', 'a lot', 'tremendously') for a total score that varies between 0 and 128. The difference in proportions of subjects achieving an ≥ 11 -point change from baseline in IQoL-32 scores will be compared at Week 12 (between TMB-001 0.05% and vehicle treatment groups) and at Week 24 (between TMB-001 0.05% BID and QD maintenance dosing groups) computed based on the CMH method (stratified by CI type), along with 95% Wald confidence intervals. No imputation will be performed for missing Week 12 or Week 24 data. Results will be provided using the primary efficacy data presentation for the Week 12 analysis, and open-label dosing efficacy data presentation for the Week 24 analysis. Only subjects that are ≥ 16 years of age will be included in these analyses.

The Week 12 analysis will be repeated using the PP population. Additionally, the difference in proportions at Week 24 will be compared against Week 12, where 95% Wald confidence intervals will be provided.

Sensitivity analyses will be performed for both Week 12 and Week 24 analyses, where questions pertaining to areas of the body where TMB-001 is explicitly not administered (e.g., eyes, ears, and scalp) will be omitted. Questions 6, 7 and 14 of the IQoL-32 will

be removed from the analysis, and the total score for this sensitivity analysis will vary between 0 and 116.

5.4.2 DLQI/CDLQI Responders at Week 12 and Week 24

The difference in proportions of subjects achieving an ≥ 4 -point change from baseline in DLQI/CDLQI scores will be compared separately for adult and pediatric subjects at Week 12 (between TMB-001 0.05% and vehicle treatment groups) and at Week 24 (between TMB-001 0.05% BID and QD maintenance dosing groups) computed based on the CMH method (stratified by CI type), along with 95% Wald confidence intervals. Adult subjects will be compared using the DLQI scores among adults with baseline scores of ≥ 11 , and pediatric patients will be compared using the CDLQI scores among pediatric subjects with baseline scores of ≥ 13 . No imputation will be performed for missing Week 12 or Week 24 data. Results will be provided using the primary efficacy data presentation for the Week 12 analysis, and open-label dosing efficacy data presentation for the Week 24 analysis.

Additionally, the difference in proportions at Week 24 will be compared against Week 12, where 95% Wald confidence intervals will be provided.

5.4.3 WI-NRS Responders at Week 24

The difference in proportions of subjects achieving a ≥ 4 -point improvement from baseline in weekly Worst Itch-QoL scores on the WI-NRS will be compared at Week 24, between the TMB-001 0.05% BID and QD maintenance dosing groups, computed in a similar manner as the primary efficacy endpoint using the CMH test, including the use of 50 multiply imputed datasets combined using the Wilson-Hilferty transformation for the pooled CMH statistic and Mantel-Haenszel stratum-weighted difference in proportions combined using Rubin's rule., along with 95% confidence intervals. Only subjects with baseline WI-NRS scores of ≥ 7 will be included in this analysis.

Unlike what is described in section 5.2.2.4, daily scores are not computed post-Week 12 visit, and so the difference in proportion at Week 24 will be computed using the results collected on Week 24, compared to baseline. In addition, the difference in proportions at Week 24 will be compared against Week 12, where 95% confidence intervals will be provided. Both analyses will be performed using multiply imputed data.

The analysis will be repeated using observed data only. The Mantel-Haenszel stratum-weighted estimator of the difference in proportion and the associated standard error will be used to produce a 95% confidence interval.

Results will be provided using the open-label dosing efficacy data presentation.

For completeness, a descriptive analysis of the I-NRS will also be provided, as applicable.

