Study Design	
This randomized, double-blind, vehicle-controlled Phase III study is designed to evaluate the efficacy and safety of topical TMB-001 0.05% ointment for the treatment of recessive X-linked ichthyosis (RXLI) and autosomal recessive congenital ichthyosis (ARCI). In addition, a subset of preselected centers will recruit subjects in parallel for enrollment into an Optional Maximal Use arm for evaluation of the systemic exposure and safety of topical TMB-001 0.05% ointment for the treatment RXLI or ARCI.
 
The study has three periods:
 
 Period 1 – Induction (3 weeks): At the beginning of the 3-week induction period, eligible subjects will be randomized (2:1 ratio) to either TMB-001 0.05% once-a-day (QD) or Vehicle QD treatment, with use of mandatory standardized bland emollient (Cetaphil™) provided by the Sponsor. Period 2 – Treatment (9 weeks): The dosing frequency in the 9-week treatment period will be increased in each treatment group to TMB-001 0.05% or Vehicle twice a day (BID). Mandatory bland emollient will be discontinued. Period 3 – Maintenance (12 weeks): At Week 12, eligible subjects in the TMB-001 treatment group will be randomized (1:1 ratio) to open-label treatment with TMB-001 0.05% BID or QD. To be eligible, subjects must have achieved a ≥ 1-point reduction in Investigator Global Assessment (IGA) score from Baseline. Subjects with < 1-point reduction in IGA score from Baseline will be discontinued from the study. Vehicle-treated subjects who achieved < 1-point reduction in IGA score from Baseline are eligible to cross over to the TMB-001 0.05% BID treatment group. Subjects with a ≥ 1-point reduction in IGA score from Baseline will be discontinued from the study. 
Optional Maximal Use Arm
 
Adult and pediatric subjects, at a subset of preselected centers, will be enrolled in an open-label Optional Maximal Use arm to evaluate the systemic exposure and safety of topical TMB-001 0.05% ointment for the treatment of CI under maximal use conditions.
 
Initially, adult CI subjects (≥ 17 years; n=16) and pediatric subjects (12-16 years; n=7-9) will be dosed for 14 days with TMB-001 0.05% BID. Following an interim pharmacokinetic (PK) analysis and based on the exposure data for subjects aged ≥ 12 years, pediatric subjects aged 6 to 11 years (n=7-9) will begin dosing with TMB-001 0.05% BID for 14 days. Following the 14-day PK assessment period, subjects will

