1.3.2 Randomization Methodology

For the initial randomization in Period 1, up to 110 subjects are planned to be randomized in a 2:1 ratio to receive either TMB-001 0.05% or vehicle. Randomization will be stratified by age group (6-11 years, 12-16 years, ≥ 17 years), and genetic subtype (RXLI, ARCI). Randomization will be performed using a permuted block design with block sizes of 3 and 6 within each stratum.

For the randomization in Period 3, all subjects initially randomized to TMB-001 0.05% are planned to be randomized in a 1:1 ratio to receive either TMB-001 0.05% BID or QD. Up to 74 subjects can be randomized, based on their responder status, defined as having a ≥ 1 -point reduction in IGA score from Baseline at the Week 12 visit. No stratification factors are planned for this portion of the study. Randomization will be performed using a fixed block design with block sizes of 4.

Both randomizations will be performed centrally by 4G Clinical through their Interactive Response Technology (IRT).

The Optional Maximal Use arm is open-label and does not require randomization.

Full details can be found in the Randomization Plan.

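### The Week 24 against Week 12 comparison of patient-reported responses has no defined contrast, subject set or pairing, and for itch it sets a one-day score against a 7-day mean

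*SAP*

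**What the plan says.** SAP 5.4.1 and 5.4.2 define two analyses each: TMB-001 against vehicle at Week 12, and BID against QD at Week 24. Both sections then add "Additionally, the difference in proportions at Week 24 will be compared against Week 12, where 95% Wald confidence intervals will be provided". Section 5.4.3 (worst itch, WI-NRS) plans the same comparison with 95% intervals on multiply imputed data. None of the three says which subjects form the Week 12 side, or whether the interval allows for the same subject being measured twice.

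The default set for SAP 5.4 is: "All analyses will be primarily performed using the ITT population, unless otherwise noted". ITT carries no condition on Week 12 response. Entry to Period 3 does. For TMB-001 subjects the protocol synopsis says: "To be eligible, subjects must have achieved a ≥ 1-point reduction in Investigator Global Assessment (IGA) score from Baseline". The others leave: "Subjects with < 1-point reduction in IGA score from Baseline will be discontinued from the study". Vehicle subjects are selected in the opposite direction: "Vehicle-treated subjects who achieved < 1-point reduction in IGA score from Baseline are eligible to cross over to the TMB-001 0.05% BID treatment group". SAP 1.3.2 on the second randomization: "Up to 74 subjects can be randomized, based on their responder status".

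The itch measure changes between visits. For Week 12, SAP 5.2.2.3 states that "daily scores of the 6 days prior to the Week 12 visit will be averaged with the daily score reported on the Week 12 visit", with at least 4 daily scores required. For Week 24, SAP 5.4.3 states that "daily scores are not computed post-Week 12 visit, and so the difference in proportion at Week 24 will be computed using the results collected on" that visit.

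**The concern.** The patient-reported objective covers both the 12-week treatment period and the 12-week maintenance period, so a Week 24 against Week 12 figure invites a reading about whether benefit held, grew or faded. As written, the figure may be uninterpretable. It may also move for reasons unrelated to any change in the subjects: a different mix of people at the two visits, a different way of scoring itch, or both. If the same people are meant, the two proportions are correlated, and a Wald interval that treats them as independent would be wrong.

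**Working it through.** The SAP gives no figure for this comparison, so there is none to reproduce. The documents also give no patient-reported response rates, no rate of 1-point IGA improvement and no day-to-day itch SD. Every size below therefore rests on assumed values.

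**1. Literal reading (5.4.1, 5.4.2).** The quantity is (p_BID - p_QD at Week 24) - (p_TMB - p_vehicle at Week 12). If the two maintenance regimens do equally well, the first bracket is zero whether benefit was fully kept or fully lost. What remains is minus the Week 12 drug effect, so the result carries no information on maintenance.

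**2. Response-rate reading with ITT at Week 12.** Let f be the share of TMB-001 subjects who continue, and r_c and r_n the Week 12 patient-reported response in those who do and do not. With no change after Week 12:

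- Week 12 rate, all subjects: f·r_c + (1-f)·r_n
- Week 24 rate, continuers only: r_c
- Apparent gain: (1-f)(r_c - r_n)

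Assume f = 0.6 to 0.8, r_c = 0.5 to 0.6, r_n = 0.2 to 0.3.

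| f | r_c | r_n | Week 12, all | Week 24 | Apparent gain |
|---|---|---|---|---|---|
| 0.8 | 0.5 | 0.3 | 0.46 | 0.50 | 0.2 × 0.2 = 4 points |
| 0.8 | 0.6 | 0.2 | 0.52 | 0.60 | 0.2 × 0.4 = 8 points |
| 0.6 | 0.5 | 0.3 | 0.42 | 0.50 | 0.4 × 0.2 = 8 points |
| 0.6 | 0.6 | 0.2 | 0.44 | 0.60 | 0.4 × 0.4 = 16 points |

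The range is 4 to 16 points. It is zero if r_c = r_n, or if the same subjects form both sides. IQoL-32 and DLQI/CDLQI are not imputed, so their Week 24 rates come only from subjects who entered Period 3. For WI-NRS, the Week 24 imputation model (SAP 3.9.1) uses BID or QD as its treatment term, and a subject discontinued at Week 12 has neither.

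**3. Itch: one day against 7 days.** The mechanism shows in a simple normal model: baseline 8, later mean level m at both visits, between-subject SD 1.5, day-to-day SD w. Response means a score of 4 or lower.

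- 7-day mean: Φ[(4-m)/√(1.5² + w²/7)]
- One day: Φ[(4-m)/√(1.5² + w²)]

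With w = 1.5:

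| Mean improvement (8-m) | 7-day rate | One-day rate | One-day, integer score (cut 4.5) |
|---|---|---|---|
| 3 | 0.266 | 0.319 | 0.407 |
| 4 | 0.500 | 0.500 | 0.593 |
| 5 | 0.734 | 0.681 | 0.760 |

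Extra daily noise pulls the rate toward 50%: up when mean improvement is below the 4-point cut, down when it is above. Integer scoring adds an upward push. Over w = 1 to 2 and m = 3 to 6, this model gives differences of about -7 to +10 points on a continuous scale and about 0 to +16 points with integer scores.

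A simulation closer to the planned analysis draws baseline from mean 6.5, SD 1.5. It keeps subjects with baseline 7 or more (single day or weekly mean), gives improvement an SD of 2 and daily scores an SD of 1 to 2, uses integer scores, and lets nothing change after Week 12:

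- Mean improvement 2 to 3: the one-day rate exceeds the 7-day rate by about 3 to 8 points, for example 0.251 against 0.329, 0.191 against 0.245, and 0.333 against 0.362. The lower end falls to about 2 points under some ways of truncating scores at 0 and 10.
- Mean improvement 4 to 5: about -3 to +6 points. The negative values arise mainly when baseline is a weekly mean.

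**The case against.** A reader might infer that the SAP deliberately sets an IGA-selected Week 24 group against the unselected Week 12 population, and so will show a false rise. The documents do not say this. ITT is only the section default. Section 5.4.3 puts its results in the open-label presentation, whose columns hold only Period 3 subjects, and that points to the same subjects at both visits. If so, the selection term is zero. This stands, and it is why the point is an undefined comparison rather than a demonstrated bias. It does not settle 5.4.1 and 5.4.2, where the primary layout is assigned to Week 12, the open-label layout to Week 24, and none to the comparison between them. Nor does it supply the pairing.

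A reader might also infer that single-day scoring always inflates itch response. It does not: the sign depends on the unknown effect size and on how baseline was scored.

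Other points in the plan's favor stand:

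- The comparison is not among the endpoints in SAP 1.4.4 or the protocol's endpoint tables, and SAP 5.4 intends no formal inference on patient-reported outcomes.
- The SAP openly states that daily itch scores stop after Week 12.
- SAP 3.11.2 already gives vehicle crossovers their own column, although it also pools them with re-randomized subjects in a total BID column.
- Precision is poor. With all 74 re-randomized and analyzable, 37 per arm at a 50% rate gives a 95% half-width of 1.96 × √(0.25/37) = 16 points. The SAP addendum reports unexpectedly few subjects above the original itch and DLQI/CDLQI baseline thresholds.

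**Conclusion.** The point holds as a defect of definition in all three sections, plus an explicit measurement mismatch for itch. Read literally, the comparison in 5.4.1 and 5.4.2 is uninterpretable. Read as response rates under the ITT default, selection alone could add about 4 to 16 points to the TMB-001 rate on the assumed values, and nothing if the same subjects are used or patient-reported response is unrelated to the IGA condition. The itch mismatch does not depend on which subjects are meant. With no true change it is worth about +3 to +8 points at mean improvement 2 to 3 and about -3 to +6 points at 4 to 5, again on assumed values.

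The consequence is modest. This is a descriptive add-on, and the primary, key secondary and Week 24 BID-versus-QD analyses do not depend on it. The documents do not support reading it as a threat to the trial's main conclusions.

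**What to change.** In SAP 5.4.1 to 5.4.3, replace the comparison sentence with a defined one:

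- **Subjects:** re-randomized TMB-001 subjects with data at both visits. Do not use the pooled total BID column here, because it mixes in vehicle crossovers.
- **Estimate:** within-subject change in responder status from Week 12 to Week 24, separately for BID and QD, with paired 95% intervals. With b subjects gaining and c losing response out of n, the change is (b-c)/n with standard error √[(b+c) - (b-c)²/n]/n. Then give the BID-QD difference in that change.
- **WI-NRS:** in this comparison only, use the Week 12 visit-day score against the Week 24 score. Keep the weekly mean for the key secondary endpoint.
- **Carry-over:** apply the same definition to the addendum's analyses with baseline scores of 4 or more. Correct the reference in 5.4.3 to section 5.2.2.4, which does not exist; the daily-score rule is in 5.2.2.3.

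The cost is SAP wording and a small programming change, with no new data. The downsides are fewer subjects on the Week 12 side, a noisier Week 12 itch score, and the loss of some subjects who have a valid weekly mean (4 or more daily scores) but no visit-day score. For WI-NRS this becomes an observed-case comparison in place of the imputed one now described.
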